## 8. CRITERIA FOR EVALUATION AND ENDPOINT DEFINITION

### 8.1 Primary Endpoint

To determine study feasibility, recruitment, accrual, retention, and adherence rates will be calculated as follows:

**Recruitment.** To determine recruitment rate, we will track number of individuals who met all eligibility criteria and percent who agree to participate.

**Accrual.** Accrual rates will be calculated by calculating the mean number of participants recruited per month.

**Retention.** Study retention will be estimated by the proportion of participants who complete the Week 13 visit. Drop-out is defined as 100% minus the dropout %.

**Adherence.** Intervention adherence will be estimated as the mean percentage of therapy (high-intensity intervention) or check-in (low-intensity intervention) sessions each participant completes.

The Working Alliance Inventory will be summarized with descriptive statistics to describe the therapist-participant relationship as a process measure

### 8.2 Secondary Endpoints

#### 8.2.1. Depression and Anxiety Measures

The **PHQ-9** is a self-report measure of DSM-IV symptoms of Major Depressive Disorder. Participants rate how often they have experienced nine symptoms over the past 2 weeks on a scale of 0 (not at all) to 3 (nearly every day). Responses are summed, with higher scores indicating greater depressive symptomatology. It has demonstrated good reliability and validity. The traditional cutoff for the PHQ-9 is a score  $\geq 10$ . However, ASCO guidelines recommend using a score  $\geq 8$ , based on a study of cancer outpatients and a meta-analysis of use of the PHQ-9 for identifying depression in cancer patients.

The **GAD-7** is a self-report measure of DSM-IV symptoms of GAD. Participants rate 7 questions on a scale of 0 (not at all) to 3 (nearly every day); one additional question assesses the interference of these symptoms with functioning. The first 7 questions are summed to create a total score. It has been validated for use in the general population and in primary care. The GAD-7 has demonstrated good sensitivity (89%) and specificity (82%) in identifying GAD diagnoses when using a cut point of 10. It also has good internal consistency (alphas = 0.89-0.92) and test-retest reliability (intraclass correlation = .83).

#### 8.2.2. Quality of Life and Symptom Measures:

The Fear of Cancer Recurrence Inventory (FCRI; severity subscale) will be used to measure self-reported fear of recurrence. This 9-item subscale measures the presence and severity of the intrusive thoughts or images associated with the fear of recurrence, and it can be used separately as a short form of the 42-item FCRI for the brief screening of fear of cancer recurrence. The measure is widely used and has strong reliability and validity (Cronbach's  $\alpha=0.75$ ).

The **Insomnia Severity Index (ISI)** is 7-item self-report measure of type and severity of insomnia symptoms, including problems with sleep onset, sleep maintenance, or early morning

awakening; satisfaction with current sleep pattern; interference with daily functioning; noticing impairment attributed to sleep problems; and level of concern or distress caused by the sleep problem. Responses are summed, with higher scores indicating greater sleep impairment. It has demonstrated reliability and validity in screening primary care patients for insomnia.

The **PROMIS Fatigue Short Form** is a measure of the experience of fatigue and the impact of fatigue on activities across multiple domains. Seven items are rated on a scale of 1(never) to 5 (always) based on how often it was experienced over the last 7 days.

The **SF-36** is a self-report measure of quality of life consisting of 36 items that form 8 subscales: physical functioning, role limitations due to physical health problems, role limitations due to emotional health problems, social functioning, freedom from pain, energy or fatigue, emotional well-being, and general health perceptions. These 8 subscales are also combined into two domains: the Physical Component Summary (PCS) and the Mental Component Summary (MCS). All of these scales range from 0 (maximum impairment) to 100 (no impairment). All scales range from 0 (maximum impairment) to 100 (no impairment). It has demonstrated good internal validity and construct validity.

**The Impact of Events Scale – Revised (IES-R)** is a 22-item self-report measure of cancer-related distress. It is one of the most widely used measures of event-specific distress. The IES-R assesses the frequency with which respondents experience intrusive thoughts, avoidant behaviors, and autonomic arousal specific to one's thoughts and feelings about cancer over the past week.

### **8.2.3. Health Care Utilization**

The **Cornell Services Index** is a structured interview that assesses the frequency of use of medical outpatient visits, psychiatric and psychotherapeutic visits, and intensive services such as hospitalizations, emergency room visits, and home health visits. The services assessed in the Cornell Services Index are aggregated into outpatient psychiatric or psychological services, outpatient medical services, professional support services, and intensive services.

### **8.2.4. Implementation Costs**

Tracking logs will measure the time spent in intervention-related activities such as bi-weekly check-in phone calls and therapy sessions with participants in stepped care, related to implementation. Tracking logs should be entered within 1-2 days of intervention-related activities; however, sites have up to 30 days to enter this information. NCORP Research Base Staff will keep an internal record of staff meetings, phone charges, mailing and printing costs and therapist training.

## **8.3 Off-Study Criteria**

Participants may go 'off-study' for the following reasons: the protocol intervention and any protocol-required follow-up period is completed, serious adverse event, lost to follow-up, withdraw consent, PI removes from study, or death.

For subjects who are enrolled, site staff must contact the subject at the next study visit with at least 5 attempts. After 5 documented contact attempts the subject will be considered lost to follow-up. Site staff must complete a Participant Status Change Form (Appendix 23) in the Telehealth website.

## **8.4 Study Termination**

NCI/DCCPS as the study sponsor or the Wake Forest NCORP Research Base has the right to discontinue the study at any time.

**9. CORRELATIVE/SPECIAL STUDIES- N/A**

**10. SPECIMEN MANAGEMENT- N/A**

**11. REPORTING ADVERSE AND SERIOUS ADVERSE EVENTS**

**11.1 Reportable Adverse Events**

An adverse event (AE) is defined as any untoward or unfavorable medical occurrence in a human subject, including any clinically significant abnormal sign (for example, abnormal physical exam or laboratory finding), symptom, or disease, temporally associated with the subject's participation in the research, whether or not considered related to the subject's participation in the research. The burden of collecting and reporting data on every possible AE is excessive and therefore, in Telehealth, sites will report all serious adverse events (SAEs) described in Section 11.2 and selected AEs listed in Section 11.3.

SAEs and AEs will be ascertained by site staff for all participants at Weeks 7 and 13. Telehealth staff will administer the Adverse Event Ascertainment Form (Appendix 22) to specifically query participants about safety events at weeks 7 and 13. In addition, adverse events may also be reported to study staff spontaneously through telephone calls, emails or other correspondence. In addition to local reporting requirements, all SAEs and selected AEs will be recorded on the Adverse Event Form by clinic staff. SAEs occurring during the study should also be reported for all participants to CTEP-AERS (see section below).

AEs will be assessed according to the grade associated with the CTCAE term. AEs that do not have a corresponding CTCAE term will be assessed according to the general guidelines for grading used in the CTCAE v5.0.. A copy of the CTCAE can be found at

[http://ctep.cancer.gov/protocolDevelopment/electronic\\_applications/ctc.htm](http://ctep.cancer.gov/protocolDevelopment/electronic_applications/ctc.htm)

**11.2 Serious Adverse Events**

**Definition:** Regulations at 21 CFR §312.32 (revised April 1, 2014) define an SAE as any untoward medical occurrence that at any dose or intervention level has one or more of the following outcomes:

A Serious Adverse Event (SAEs) is defined if it results in **ANY** of the following outcomes:

- Death
- Life-threatening
- Results in inpatient hospitalization or prolongation of existing hospitalization for  $\geq$  24hours
- A persistent or significant incapacity or substantial disruption of the ability to conduct normal life functions
- A congenital anomaly/birth defect
- Important Medical Event (IME) that may not result in death, be life threatening, or require hospitalization may be considered serious when, based upon medical judgment, they may jeopardize the patient or subject and may require medical or surgical intervention to prevent one of the outcomes listed in this definition. (FDA, 21 CFR 312.32; ICH E2A and ICH E6).

**Reporting Requirements for above Study Descriptions:**

- All unexpected hospitalizations regardless of grade
- All Grade 5 toxicities (deaths-expected and unexpected)
- All unexpected Grade 4 toxicities
- All additional reporting requirements as outlined in the protocol

Serious adverse events as described above must be reported on the Telehealth Adverse Event Form and also be reported to CTEP-AERS:

CTEP-AERS (Research Base Data Management) reporting timelines are defined as:

- Deaths or life threatening events (Grades 4-5): 24-Hour; 5 Calendar Days - The SAE must initially be reported via CTEP-AERS within 24 hours of learning of the SAE, followed by a complete expedited report within 5 calendar days of the initial 24-hour report.
- Hospitalizations, disabling, important medical events (IME) that may not result in death, be life threatening, or require hospitalization (Grade3) and study specific adverse events: 10 Calendar Days - A complete expedited report on the SAE must be submitted within 10 calendar days of learning of the SAE.

## **11.3 Selected Adverse Events**

A select list of adverse events include suicide attempts, psychosis, worsening anxiety, worsening depression, and suicidal ideation, should be reported as an adverse event, regardless of whether they resulted in an ER visit or hospitalization.

### **11.3.1. Definition of Worsening Anxiety or Depression**

An adverse event form should be completed for any participant who indicates a significant worsening in anxiety or depression scores (1 standard deviation increase (rounded to the nearest integer) on the GAD-7 (Change $\geq 4$ ) or PHQ-9 (Change $\geq 6$ ) from baseline). The computer software system will automatically generate an e-mail to the co-PIs and the project manager. If there is a need for immediate treatment (e.g., active suicidal ideation, active psychotic symptoms, disorientation, and active substance abuse) at any point in time, staff persons will notify the co-PIs. In both cases, the participant may be referred for psychiatric care.

## **12. STUDY MONITORING**

### **12.1 Data Management**

The Enrollment Form should be completed on-line at randomization. Data will be entered directly into the study website. The PHQ-9 and GAD-7 must be entered into the Telehealth website within 48 hours of being administered. The Crisis Protocol form (Appendix 21) must be entered into the Telehealth website at the time the form is completed with the participant. Refer to Section 11 for submitting the Adverse Event form. All other assessments must be completed within the designated study visit windows then data entered into the Telehealth website by designated site staff or designated study therapist within 14 days from the date assessments are completed.

### **12.2 Case Report Forms**

Participant data will be collected using protocol-specific case report forms (CRF).

### **12.3 Source Documents**

The sources of research material will include information provided through participant interviews, intervention sessions, and self-report questionnaires specifically for this research study. A number of steps will be taken to ensure the confidentiality of research data collected during the study. The study will obtain a Certificate of Confidentiality which prevents researchers from being forced to disclose identifying information by certain legal proceedings. All forms will be stored in locked file cabinets.

Names will be removed from all forms and records and replaced with participant numbers. Recorded sessions will be erased upon completion of data collection. Information stored in the computer will be password protected. Only members of the investigative team will have access to any participant information and data. The identities of participants will not be revealed in publications and presentations of any results from this project. Procedures specified in the consent form are consistent with HIPAA regulations. All investigators have completed NIH-required training in human subjects protection.

An investigator and other designated staff are required to prepare and maintain adequate and accurate documentation that records all observations and other data pertinent to the investigation for each individual participating in the study. All data recorded in the research record (including data recorded on CRFs) must originate in the participant's medical record, study record, or other official document sources.

Source documents substantiate CRF information. All participant case records (e.g., flow sheets, clinical records, physician notes, correspondence) must adhere to the following standards:

- Clearly labeled in accordance with HIPAA practices so that they can be associated with a particular participant identification number (PID);
- Legibly written in ink;
- Signed and dated in a real time basis by health care practitioner evaluating or treating the participant; and
- Correction liquid or tape must not be used in source documents or on CRFs.
- Corrections are made by drawing a single line through the error. Do not obliterate the original entry. Insert the correct information, initial, and date the entry.

## **12.4 Data and Safety Monitoring Plan**

The Comprehensive Cancer Center Data Safety Monitoring Board meets every six months to review all phase II and phase III protocols. The Board includes members demonstrating experience and expertise in oncology, biological sciences, biostatistics, pastoral care/counseling, and ethics. The members of this committee as well as the organization statistician will oversee the safety monitoring of the study, ensure that the privacy of all participants in the study is protected and ensure that participants' interests are primary, that is, above the interests of the scientific investigation. Adverse events will be elicited by study staff during assessments and check-in calls for the EUC group and by the study therapists during each session. Information about any adverse events will be presented. By examining this information, the data and safety monitoring team will keep abreast of critical issues regarding recruitment and data integrity. Reports of all DSMB meetings and recommendations will be provided to the NCI and WFUSM IRB.

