## 7. CLINICAL EVALUATIONS AND PROCEDURES

### 7.1 Intervention Description

Participants with moderate anxiety and depressive symptoms will be randomized to either the low-intensity stepped-care telehealth or the EUC control. Participants with severe symptoms will be randomized to either the high-intensity stepped-care telehealth intervention or the EUC control. Therapists participating in the trial must meet the following requirements: a Master's or doctoral degree in counseling, marriage and family therapy, psychology, or social work; licensed as an independent mental health provider in California, Georgia, Illinois, Kansas, Michigan, Minnesota, Missouri, New Mexico, North Carolina, North Dakota, South Carolina, Virginia, Tennessee, or Wisconsin; and experience with cognitive-behavioral therapy. Experience working with oncology patients/survivors is preferred. Therapists will attend a 1.5-day training that will cover information on study design, anxiety and depression in cancer survivors, principles of cognitive-behavioral therapy, delivery of the intervention, and use of the web-based data-entry system. NCORP sites and/or components may nominate therapists for participation, but are not required to identify a therapist to participate. The Wake Forest study team will identify a participating therapist for each state.

Low Intensity Stepped-care Telehealth: The low-intensity stepped-care telehealth group will consist of a self-guided CBT workbook (15 minutes daily to read and complete exercises/homework) and biweekly (every two weeks) check-in calls (5-10 minutes) from an NCORP component research staff person to assess changes in symptom severity/immediate need for psychiatric treatment and provide minimal support. Check-in calls are expected to be completed within +/- 2 days of the window specified in the Telehealth website; however, check-in calls up to +/- 1 week of the window are permitted.

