High Intensity Stepped-care Telehealth: The high-intensity stepped-care telehealth group will consist of the CBT workbook (15 minutes daily to complete exercises/homework), plus psychotherapy delivered by telephone with a licensed therapist (45 minute sessions weekly). If participant is randomized to the High

Intensity Arm, the therapist will make at least one attempt to schedule the participant's first therapy session within 2 weeks of the date of notification via email.

Consistent with the ASCO guidelines, the Wake Forest NCORP Research Base staff will mail a professionally prepared and IRB approved CBT workbook to participants and participants will have 12 weekly therapy sessions with the study therapist. The study therapist will be a licensed mental health provider (e.g., licensed clinical social worker, marriage and family therapist, licensed professional counselor, psychologist). Onsite or phone training is provided for all participating therapists. Training will include the use of the workbook, formal didactic presentations, readings, and role-plays. All study therapists will receive regular (at least monthly) study supervision from [name]. There will be at least one trained therapist for each state in the U.S. that has any participating sites. Each week, the participant will receive one 45-minute telephone session and one workbook chapter. The sessions will supplement the participant's understanding of anxiety, depression, and distress management techniques and include a review of the daily workbook exercises to assure understanding and maximize application in daily life.

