## Study Parameter Table

	Recruitment/ Chart Review	Pre-Screen	Verbal Consent	Full Screen	Full Informed Consent	Baseline	Enrollment/ Randomization (wk0)	Weeks 1-13			Post Week 13
								Wk1 or 2	W7	W13	
NCORP Component Site Staff Responsibility											
Mail Recruitment Documentation*	As needed										---
Pre-Visit Form (Appx 2)	X										---
Pre-Screening Form (Appx 3)*		X a									---
Abbreviated Verbal Consent			X a								---
Screening Form (Appx 4)*				X a							---
Full Informed Consent					X a						---
Baseline Self-Report Letter and Measures (Appxs 5a+b)*						X a					---
Baseline Interviewer-Administered Measures and Chart Review (Appx 6)*							X a				---
Letter to Ineligible Participants (SD 2)		As Needed									---
Enrollment Form (Appx 7)							X				---
Randomization Form (Appx 8)							X b				---
EUC Randomization*							X		X		EUC
Expectancy Rating Scale and Letter  (Appxs 10a+b)							X				LISC/ HISC
Low Intensity Check-In Call Form (Appx 14)								Biweekly (wks 2/4/6/8/10/12)			LISC
Upload audio recordings								Biweekly (wks 2/4/6/8/10/12)			LISC
Week 7 Mid-Assessment Interviewer-Administered Measures (Appx 11)*									X		All
Week 13 Self-Report Letter and Measures (Appxs 12a+b)*										X	All
Week 13 Interviewer-Administered Measures (Appx 13)*										X c	All
Participant Completion Letter (SD 3)/Resource Sheet (SD 9)										X	LISC/ HISC
Participant Change Status Form (Appx 23)								As Needed			All
Adverse Event Form (Appx 22)		As Needed									All
Crisis Protocol Event Form (Appx 21)		As Needed									All
Tracking Log (Appx 24)		To be completed for each attempted contact and actual contact									All
Wake Forest Research Base Responsibility											
EUC Randomization*							X				EUC
Investigator adherence rating forms (Appx 18 and 19)*								As needed			LISC/ HISC
Mail Recorder							As needed				LISC/ HISC
Mail CBT Booklet							X				LISC/ HISC
Mail CBT Booklet										X	EUC
Study Therapist Responsibility											
Weekly Therapist activities (Appxs 15-17) recordings*								Weekly (wks 1-13)			HISC
Tracking log		To be completed for each attempted contact and actual contact									HISC

Abbreviations: Appx=Appendix, EUC=Enhanced Usual Care, HISC=High-Intensity Stepped-Care Arm, LISC=Low-Intensity Stepped-Care Arm

\* See appendix 26 for details

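### Section 12.4 credits EUC with check-in calls it does not receive and adds AE elicitation at every therapy session, so by-arm counts of non-serious, transient AEs are open to ascertainment bias

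*Combined protocol and SAP*

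**What the plan says.** Section 12.4 (Data and Safety Monitoring Plan) describes two routes for finding AEs. The first is: "Adverse events will be elicited by study staff during assessments and check-in calls for the EUC group". The second is "and by the study therapists during each session". The low-intensity arm is not named in that passage.

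Section 11.1 describes something different: "SAEs and AEs will be ascertained by site staff for all participants at Weeks 7 and 13", using the Adverse Event Ascertainment Form. It adds that "adverse events may also be reported to study staff spontaneously through telephone calls, emails or other correspondence". It does not mention elicitation at therapy sessions or check-in calls.

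Section 7.1 places the calls in the low-intensity arm: "biweekly (every two weeks) check-in calls (5-10 minutes) from an NCORP component research staff person to assess changes in symptom severity". The Study Parameter Table schedules the call form as "Biweekly (wks 2/4/6/8/10/12") in the low-intensity row, and Sections 3 and 8.1 agree. For high intensity, Section 7.1 says "participants will have 12 weekly therapy sessions with the study therapist". EUC receives resource and referral information, letters, questionnaire reminders and the common assessments (Sections 3, 4.4, 7.1, 7.2 and 7.6).

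**The concern.** There are two linked problems. First, Section 12.4 describes monitoring of the control arm through a contact that the rest of the protocol does not provide. EUC participants enter with moderate or severe symptoms, so an oversight board should be told accurately how often they are asked about harm.

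Second, the selected AEs in Section 11.3 include suicidal ideation and psychosis. These can come and go between visits and are often found only by asking. If one arm is asked at up to 14 scheduled contacts and another at 2, the first can record more such events at the same true rate. Section 12.4 says AE information will be presented, and Section 2.2 says the study is meant to inform a larger trial. A by-arm table of these events could therefore be read as a difference in harm when part of it is a difference in how often people were asked.

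**Working it through.** **Number of sessions and calls.** The documents give no count of AE contacts per arm, but Section 5.3 allows a check on the intervention contacts. One reviewed session per participant is put at 8% of therapy sessions, and 1/12 = 8.3%. One reviewed call is put at 16% of calls, and 1/6 = 16.7%, so the stated figure looks truncated. This agrees with 12 sessions (7.1) and 6 calls (Study Parameter Table).

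**Scheduled eliciting contacts per participant, with full attendance:**

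- High intensity: 12 sessions + 2 assessments = 14.
- EUC: 2 assessments = 2.
- Low intensity, literal reading: 2. Section 12.4 does not name this arm, and 7.1 states no general AE query at the calls.
- Low intensity, inferred reading: 6 calls + 2 assessments = 8. The inference is reasonable because, under Section 3, the call form covers symptom change over the past two weeks and leads to the crisis protocol for suicidal ideation.

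**By randomised comparison.** Section 13.2 plans 50 moderate and 40 severe participants, randomised equally within stratum. That gives 25 low intensity, 20 high intensity and 45 EUC (25 moderate, 20 severe).

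| Comparison | Stepped care | EUC | Ratio |
|---|---|---|---|
| Severe stratum | 20 × 14 = 280 | 20 × 2 = 40 | 7 |
| Moderate stratum, literal | 25 × 2 = 50 | 25 × 2 = 50 | 1 |
| Moderate stratum, inferred | 25 × 8 = 200 | 25 × 2 = 50 | 4 |
| Overall, literal | 330 | 90 | 3.7 |
| Overall, inferred | 480 | 90 | 5.3 |

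**What this could do to recorded events.** Let p be the chance that a reportable state is found at any one contact, independent between contacts and equal in all arms. The documents do not give p; it is an assumption. The share of participants with at least one recorded event is 1 − (1 − p)^k for k contacts. The pooled stepped-care share weights high and low intensity 20:25.

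| p | k = 14 | k = 8 | k = 2 | Ratio, k = 14 to k = 2 | Pooled ratio, inferred | Pooled ratio, literal |
|---|---|---|---|---|---|---|
| 0.01 | 0.131 | 0.077 | 0.020 | 6.6 | 5.1 | 3.5 |
| 0.05 | 0.512 | 0.337 | 0.098 | 5.3 | 4.3 | 2.9 |
| 0.10 | 0.771 | 0.570 | 0.190 | 4.1 | 3.5 | 2.4 |
| 0.30 | 0.993 | 0.942 | 0.510 | 1.9 | 1.9 | 1.4 |
| 0.50 | 1.000 | 0.996 | 0.750 | 1.3 | 1.3 | 1.1 |
| 0.90 | 1.000 | 1.000 | 0.990 | 1.0 | 1.0 | 1.0 |

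The literal pooled ratio is (20 × R + 25)/45, where R is the ratio of k = 14 to k = 2. For p = 0.05 this is (20 × 5.25 + 25)/45 = 2.9.

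**Look-back.** The PHQ-9 asks about the past 2 weeks (8.2.1), so two administrations cover about 2 × 2 = 4 of 13 weeks. Six calls with a two-week look-back cover about 6 × 2 = 12. The Week 7 visit may fall as late as Week 11 (7.6), so an EUC participant can wait that long for the first structured safety query after baseline.

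**Limits.** The Study Parameter Table lists therapist activity over weeks 1–13, while 7.1 gives 12 sessions; I used 12. A low-intensity participant moved to high intensity at Week 7 has a different number of contacts but stays in the initial arm for analysis.

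**The case against.** A reader might infer that by-arm counts measure contact frequency rather than harm. The documents do not support that. All arms share one structured query at Weeks 7 and 13. Worsening anxiety and depression are defined by GAD-7 and PHQ-9 change from baseline (11.3.1), and those scales are scheduled equally in all arms. Nothing in the text schedules them at therapy sessions. SAEs such as hospitalisation are less likely to be missed at the two common visits.

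A reader might also infer that events between visits go unseen in EUC. That is not established. Spontaneous reports are open to every arm, and the recall period of the ascertainment form would be in Appendix 22, which is not part of the text reviewed. A form asking about the whole interval would narrow the gap, though it would rely on memory.

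The low-intensity count of 8 is an inference: Section 7.1 gives the purpose of the calls only as "to assess changes in symptom severity/immediate need for psychiatric treatment and provide minimal support". The percentages above depend on an assumed p and on independence between contacts with the same person. High intensity enrols only severe participants, so comparing it with all of EUC is not a randomised contrast. Section 13 plans no by-arm safety test, and unequal contact is inherent in comparing therapy with usual care. It would go too far to say that the DSMB will draw a wrong conclusion, since 7.1 and the Study Parameter Table show which arm has the calls.

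All of this stands as a limit on size and certainty. It removes neither the contradiction in 12.4 nor the 14-to-2 difference in scheduled contacts.

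**Conclusion.** Section 12.4 conflicts with 7.1 and the Study Parameter Table on EUC check-in calls, and with 11.1 on when AEs are elicited. The counts of 14 (high intensity) and 2 (EUC) follow from the text under full attendance. Low intensity is 2 as written, or 8 by inference.

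By-arm counts of non-serious, transient, between-visit events are therefore open to ascertainment bias in the direction that makes EUC look safer. Its size is unknown. Under the illustrative model the pooled ratio runs from about 1, if the common visits capture nearly everything, to about 5 on the inferred reading or 3.5 on the literal one at p = 0.01. Score-defined worsening at Weeks 7 and 13 and SAEs are much less affected. The consequence is for how any by-arm AE table is read, because no formal safety comparison is planned.

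**What to change.** - Reconcile 12.4 with 7.1 and 11.1 so that it states the actual AE contacts in each arm, including whether the low-intensity calls elicit AEs.
- Record on the AE form the contact at which each event was found, if the form does not already do so.
- Base any by-arm summary of non-serious selected AEs on the common Week 7 and Week 13 ascertainment (the Adverse Event Ascertainment Form and PHQ-9/GAD-7 change). Present it by randomised arm: stepped care against EUC, overall or within severity stratum.
- Put events found at sessions, at calls or by spontaneous report in a separate table labelled as unequally ascertained.
- Summarise deaths and all other SAEs by arm whatever their source. Section 8.3 lists death, an SAE and loss to follow-up as reasons for going off study, so such an event before Week 7 or 13 might never reach the common form.
- Leave SAE reporting, alerts and crisis procedures unchanged.

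The cost is a corrected sentence in 12.4, at most one field on the AE form, and one extra table. The compared table of non-serious AEs will contain fewer events and will depend on completion of the Week 7 and 13 visits; Section 13.3 allows for 20% dropout.
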